12.2 Patient Enrollment

After signing the informed consent form, each potential subject will be screened for eligibility based on the inclusion and exclusion criteria specified. Randomization will be done.

All visits will occur as closely as possible to the scheduled visit dates with window of 3 days. In case of a premature discontinuation of the study, the subject, will be, if possible called in for a last visit. Even if the subject would not be able to attend, the 'End of Study' forms will be completed .

12.3 12.3 Schedule of visits

Table 1: Schedule of Visits

Observation	Visit 1 (Screening & treatment)	(Follow-up 1 V)	(Follow-up 2 V) End of Study
Time lines	Day 0	Day 8	Day 15
Informed consent document signed	X		
Review Inclusion/Exclusion criteria	X		
Patient Demographics	X		
Significant medical history and current disease status	X		
Physical examination	X	X	X
Vital Signs	X	X	X
Child-Pugh Score	X		
Concomitant medications	X	X	X
Safety Laboratory Tests:			
FBS	X		
Total Leucocytic count	X		X
SGOT (ALT)	X		X
SGPT (AST)	X		X
Total Bilirubin	X		X
S. Creatinine	X		X
Serum β -HCG: (for females in childbearing period)	X		
Pelvi-abdominal Ultrasound & others (Optional)	X		X
Study Drug Dispensed	X	X	
Drug Accountability		X	X

Observation	Visit 1 (Screening & treatment)	(Follow-up 1 V)	(Follow-up 2 V) End of Study
Time lines	Day 0	Day 8	Day 15
Presence of any signs/symptoms of post-operative wound infection such as redness, fever or wound discharge. (in case of post-operative subjects)	X	X	X
Days for complete healing		X	X
Complete resolution, improvement, failure or relapse of pelvi - abdominal infection		X	X
AE		X	X
SAE		X	X
Study Completion Form			X

The subsequent visits will occur as follows :

- **Visit 1 (Screening & treatment initiation Visit):** Day 0
- **Follow-up V1:** Day 8 (+/-) 3 days
- **Follow-up V2 & End of Study Visit:** Day 15 (+/-) 3 days

12.3.1 Visit 1 (Screening & treatment initiation):

- During this visit, subjects will be informed about the study. If they are willing to participate in the study, they will sign the written ICF. A copy of the signed ICF will be given to the subject. In addition, the subjects will be evaluated for study eligibility according to the inclusion and exclusion criteria.
- Screening Assessments will include: physical examination, vital signs, demographic data (Age & Gender), medical history and concomitant medications.
- Presence of any signs/symptoms of post-operative wound infection such as redness, fever or wound discharge will be recorded (in case of post-operative subjects)
- Child-Pugh Score will be calculated for liver impairment and pelvi-abdominal Ultrasound and others will be done
- Lab results will be checked for: (Fasting Blood Sugar (FBS), Total leukocytes count, liver enzymes (SGOT & SGPT), Total Bilirubin and S. Creatinine), and Serum β -HCG for females of child bearing potential only
- The Investigator will keep a log of all subjects, who will sign the ICF. Even if the subject would not pass the screening, his/her signed consent form will be retained

in the Investigator file and will be considered as screening failure. The reason(s) for screen failure will be recorded in the screen failure form in the screening log.

- All data related to screening visit must be reviewed (signed and dated) by the Investigator to ensure that the subject will be eligible for the study, before dispensing the study drug.
- Randomization will be done and subjects will be administered the study products; either Ciprofloxacin® tablets or Ciprofloxacin Tablets & Metronidazole tablets.
- Study products sufficient for the next 7 days will be supplied; either Ciprofloxacin® tablets or Ciprofloxacin Tablets & Metronidazole tablets, and storage conditions will be explained. Study products supplied will be recorded.
- Subjects will be asked to come after 7 days of treatment and bring the empty blisters of medication received, with window of 3 days.

In case of any premature discontinuation of the study, the subject will be, if possible, called in for a last visit. Even if the subject was not able to attend the last visit, the End of Study Form must be completed.

Child-Pugh Score will be recorded, as follows:

The score employs five clinical measures of liver disease. Each measure is scored 1-3, with 3 indicating most severe derangement.^[20]

Table 2: Child-Pugh Score

Measure	1 point	2 points	3 points
Total bilirubin, µmol/l (mg/dl)	<34 (<2)	34-50 (2-3)	>50 (>3)
Serum albumin, g/dl	>3.5	2.8-3.5	<2.8
Prothrombin time, prolongation (secs)	<4.0	4.0-6.0	> 6.0
Ascites	None	Mild	Moderate to Severe
Hepatic encephalopathy	None	Grade I-II (or suppressed with medication)	Grade III-IV (or refractory)

In primary sclerosing cholangitis (PSC) and primary biliary cirrhosis (PBC), the bilirubin references are changed to reflect the fact that these diseases feature high conjugated bilirubin levels. The upper limit for 1 point is 68 µmol/l (4 mg/dl) and the upper limit for 2 points is 170 µmol/l (10 mg/dl).

Chronic liver disease is classified into Child-Pugh class A to C, employing the added score from above.

Table 3: Child-Pugh Classes

Points	Class
5-6	A
7-9	B
10-15	C

The Investigator will keep a log of all subjects who will sign the consent form. Even if the subject would not pass the screening, his/her signed consent form will be retained in the Investigator file.

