After oral administration, Metronidazole is rapidly absorbed, 80 % is absorbed in one hour. The peak concentration is achieved after 1 to 2 hours after the oral administration. Metronidazole passes the placenta and the maternal milk. The serum elimination half-life in subjects is 8 hours. The essential excretion is through the liver and the bile.

The most common side effects include: allergic reactions such as skin rash, swelling of the face, lips, tongue or throat, fever or difficulty in breathing.

Metronidazole is contraindicated in case of Hypersensitivity to Metronidazole and First trimester of pregnancy, while it should be administered with caution to patients with the following conditions:

- Convulsive seizures and peripheral neuropathy
- Patients with active neurological disorders
- Decreased Neutrophils or a history of blood dyscrasias
- Prolonged QT interval on ECG
- Severe liver disease

8.4 Dosage & Administration:

8.4.1 Ciprofloxacin[®] Tablets:

The recommended dosage of ciprofloxacin[®] is 1 tablet every 12 hours for a duration not exceeding 15 days, according to the investigator's decision. The tablet should be swallowed with plenty of water.

8.4.2 Ciprofloxacin[®] Tablets:

The recommended dosage of Ciprofloxacin tablets is 500 mg every 12 hours for 7 to 14 days, according to the investigator's decision. Tablets should be swallowed with plenty of fluid, during or after meals. It is contraindicated to be taken with dairy products such as milk or yoghurt or with fortified fruit juices (e.g. calcium-fortified orange juice).

The usual dose of Ciprofloxacin should be modified in patients with severe renal impairment, as the following table of the dosage guidelines, according to the Creatinine Clearance (CrCl):

CrCl (mL/min)	Dose
> 50	Usual Dosage
30 – 50	250 – 500 mg every 12 h
5 – 29	250 – 500 mg every 18 h
Patients on hemodialysis or Peritoneal dialysis	250 – 500 mg every 24 h (after dialysis)

8.4.3 Metronidazole[®] Tablets:

Tablets should be swallowed with plenty of water, during or after meals. The recommended dose is 7.5 mg/kg every 6 hours (approx. 500 mg for a 70-kg adult every 6 hours). A maximum of 4 g should not be exceeded during a 24-hour period for 7 to 10 days, according to the investigator's decision.

For patients with severe renal impairment ($\text{CrCl} < 30$), the dose of Metronidazole[®] Tablets should be reduced by 50%

8.5 8.5 Precautions:

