8.5.2 Dispensing

The Sponsor will be responsible for providing the study drugs either Ciprofloxacin[®] Tablets (Ciprofloxacin/Metronidazole) or Ciprofloxacin Tablets & Metronidazole tablets to the patients in a quantity enough to be used till the end of the study and will record the patient's number and initials.

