12.3.2 Follow-up 1 Visit (Day 8)

It could be the end of treatment for some subjects.

The following procedures will be done this visit, and all relevant information will be recorded in the source document and forms:

- Subjects will undergo thorough general physical examination and Vital signs
- Presence of any signs/symptoms of post-operative wound infection such as redness, fever or wound discharge will be recorded (in case of post-operative subjects)
- Any changes in concomitant medication, illness and treatment will be recorded.
- Checking if any AE or SAEs happened and recording them in their separate forms.
- Days for complete healing will be checked, if happened.
- Complete resolution, improvement, failure or, relapse of Pelvi- abdominal infection will be recorded
- Subjects will be asked to come after 15 days of the treatment (Day 15) for follow up, with window of 3 days
- In case of any premature discontinuation of the study, the subject will be, if possible, called in for a last visit. Even if the subject was not able to attend the last visit, the End of Study Form must be completed.
- In case of complete resolution, end of the study lab testing will be asked and recorded and End of the study Form will be completed

12.3.3 Follow-up 2 Visit & End of Study Visit (Day 15):

It is the end of study visit for subjects.

The following procedures will be done during this visit, and all relevant information will be recorded in the source document and forms:

- Subjects will undergo thorough general physical examination and Vital signs
- Presence of any signs/symptoms of post-operative wound infection such as redness, fever or wound discharge will be recorded (in case of post-operative subjects)
- Any changes in concomitant medication, illness and treatment will be recorded.
- Checking if any AE or SAEs happened and recording them in their separate forms. Days for complete healing will be checked.
- Complete resolution, improvement, failure or, relapse of Pelvi- abdominal infection will be recorded
- Lab results will be checked for: S. Creatinine, Total leukocytes count, Liver enzymes (SGOT, SGPT), and total bilirubin
- Pelvi-abdominal Ultrasound and others will be done, if needed.
- The End of Study Form must be completed.

13 Management & Reporting of Adverse Events

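### The 7-day hand-out at Visit 1 can run out up to 3 days (4 if Day 0 counts) before a permitted late Follow-up 1 visit, interrupting courses longer than 7 days

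*Protocol*

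**What the plan says.** Protocol section 12.3.1 (Visit 1, Day 0) states that "subjects will be administered the study products" at that visit and that "Study products sufficient for the next 7 days will be supplied". It adds: "Subjects will be asked to come after 7 days of treatment and bring the empty blisters of medication received, with window of 3 days".

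Section 12.3 places Follow-up 1 at Day 8, plus or minus 3 days, so a visit on any day from Day 5 to Day 11 is within plan. In Table 1 the row "Study Drug Dispensed" is marked at Visit 1 and Follow-up 1 only. Section 12.2 says: "All visits will occur as closely as possible to the scheduled visit dates with window of 3 days".

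On course length, section 8.4.1 gives Ciprodiazole as "1 tablet every 12 hours for a duration not exceeding 15 days". Sections 8.4.2 and 8.4.3 give 7 to 14 days for ciprofloxacin and 7 to 10 days for metronidazole. In all three the investigator decides. Section 12.3.2 says of Follow-up 1: "It could be the end of treatment for some subjects". Other patients therefore continue past it.

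On overall supply, section 8.5.2 makes the sponsor responsible for providing drug "in a quantity enough to be used till the end of the study", and section 8.1 says that treatment is provided for the patient's whole duration.

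**The concern.** The first hand-out is sized to the nominal visit date and not to the end of the visit window. A site can hand out exactly 7 days of drug, see the patient on Day 11, and be fully compliant, while a patient whose course is still running has had no tablets for several days. No overage, early collection or bridging supply is described.

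Longer courses are foreseeable. Section 6 cites a 14-day course as the recommendation for pelvic inflammatory disease, which is one of the named qualifying infections.

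At stake is an unintended break in treatment of an infection that the investigator has judged to need more than 7 days. The hand-out and the window are the same in both arms.

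**Working it through.** The plan states no gap figure to reproduce, so the check is calendar arithmetic.

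**Inputs.** Supply at Visit 1: 7 days (12.3.1). First dose: at Visit 1, Day 0 (12.3.1). Latest Follow-up 1: Day 8 + 3 = Day 11 (12.3). Next dispensing: Follow-up 1 (Table 1). Dosing: Ciprodiazole and ciprofloxacin every 12 hours, 2 doses a day; metronidazole about 500 mg every 6 hours for a 70-kg adult, 4 doses a day (8.4.1 to 8.4.3).

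**Two day counts.** The protocol does not say whether Day 0 is one of the 7 days.
- If a dose is given at the visit and the hand-out covers Days 1-7, the first uncovered day is F = 8.
- If the hand-out covers Days 0-6, F = 7.

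**By visit day, course still running.** Gap = max(0, V − F), where V is the visit day and drug is taken as available again on that day.

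| Follow-up 1 on | Hand-out Days 1-7 | Hand-out Days 0-6 |
|---|---|---|
| Day 7 or earlier | 0 | 0 |
| Day 8 | 0 | 1 |
| Day 9 | 1 | 2 |
| Day 10 | 2 | 3 |
| Day 11 | 3 | 4 |

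**By course length, visit on Day 11.** With dosing from Day 0, an n-day course occupies Days 0 to n − 1. Gap = max(0, min(11, n) − F).

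| Course | Hand-out Days 1-7 | Hand-out Days 0-6 |
|---|---|---|
| 7 days | 0 | 0 |
| 8 days | 8 − 8 = 0 | 8 − 7 = 1 |
| 9 days | 9 − 8 = 1 | 9 − 7 = 2 |
| 10 days | 10 − 8 = 2 | 10 − 7 = 3 |
| 11 days or more | 11 − 8 = 3 | 11 − 7 = 4 |

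**In doses, hand-out Days 1-7.**
- Ciprodiazole, 11 days or more: 3 × 2 = 6 doses, which is 6/30 = 20% of a 15-day course or 6/28 = 21% of a 14-day course.
- Metronidazole, 10 days: 2 × 4 = 8 of 10 × 4 = 40 doses, or 20%.

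These are doses not taken on time. They are the largest values the window allows.

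**The case against.** **Supply wording.** Saying that the supply must suffice for 7 days does not forbid more. Sections 8.1 and 8.5.2 promise drug throughout, and section 8.5.1 expects partly used and unused blisters to come back. This shows that continuous supply was intended, and one might infer that the 7-day line is a hard cap, which the text does not say. But none of these sections sets an amount per visit or requires any overage, so a site that hands out 7 days is following the plan.

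**Timing.** Patients are asked to return after 7 days of treatment, and section 12.2 wants visits close to schedule. On the Days 1-7 count, an on-time Day 8 visit leaves no gap. This makes the problem less frequent, but the same sentence of section 12.2 grants the 3-day window.

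**Staged dispensing.** A short first supply followed by clinical review is a defensible choice, because some patients stop at Follow-up 1. That stands, and the second remedy below keeps it.

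**Stronger readings that the documents do not support.**
- A reader might infer that the missed doses are lost. The investigator decides the duration and no calendar stop date is fixed, so a patient seen on Day 11 can be given more drug and finish. Loss would follow only if, for example, the 15-day limit is read as calendar days and is reached.
- A reader might put the gap in a 10-day metronidazole course at 3 days, 12 of 40 doses. That holds if the hand-out includes Day 0, or if dosing starts only on Day 1. It does not hold if a dose is given on Day 0 and the hand-out covers Days 1-7, because the course then ends on Day 9. If Day 0 is a partial dosing day, the value lies between 2 and 3 days.
- A reader might infer bias between arms or a weakened efficacy result. The hand-out and window rules are common to both arms, and nothing in the documents allows an endpoint effect to be estimated.

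**Conclusion.** The point holds as a minor patient-protection issue. A protocol-compliant late Follow-up 1 visit can interrupt a continuing course by up to 3 days (hand-out Days 1-7) or up to 4 days (hand-out Days 0-6). On the second count even an on-time Day 8 visit leaves 1 day uncovered.

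The conclusion assumes that the site dispenses exactly 7 days, that the course runs beyond the supply, and that the visit falls after the supply ends. Patients on 7-day courses and those seen by Day 7 are not affected. The documents do not give the number of patients who combine a longer course with a late visit, so the frequency cannot be stated.

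**What to change.** Amend section 12.3.1 in one of two ways.

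1. **Larger first hand-out.** Dispense enough at Visit 1 to reach the end of the Follow-up 1 window: Days 1-10, which is 10 days, or Days 0-10, which is 11 days. Dispense the planned course if that is shorter. Leftovers are returned and counted.
   - Ciprodiazole: 20 or 22 tablets instead of 14, so 6 to 8 more per patient.
   - Control arm: 6 to 8 more ciprofloxacin tablets, and 3 × 4 = 12 to 4 × 4 = 16 more metronidazole doses by days of window. A 10-day metronidazole course caps that at 40 − 28 = 12, and shorter courses need fewer.
   - Downside: patients stopped at Follow-up 1 hold some surplus antibiotic.
2. **Collection before the supply ends.** Keep the 7-day hand-out, but require patients who will continue to be seen, or to collect more drug, by Day 8 (Day 7 if Day 0 counts). This needs no extra tablets up front and keeps further drug tied to the clinical review. It costs a tighter visit or a collection step, and continuing patients can no longer use the late days of the window without collecting drug first.

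Either way, state whether Day 0 is one of the 7 days, and align the instruction to return after 7 days with the Day 8 schedule. On the Days 1-7 count the two are the same date. One sentence tying section 8.5.2 to the amount dispensed at each visit would settle how the two sections fit together.

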12.3.2 Follow-up 1 Visit (Day 8)

It could be the end of treatment for some subjects.

The following procedures will be done this visit, and all relevant information will be recorded in the source document and forms:

- Subjects will undergo thorough general physical examination and Vital signs
- Presence of any signs/symptoms of post-operative wound infection such as redness, fever or wound discharge will be recorded (in case of post-operative subjects)
- Any changes in concomitant medication, illness and treatment will be recorded.
- Checking if any AE or SAEs happened and recording them in their separate forms.
- Days for complete healing will be checked, if happened.
- Complete resolution, improvement, failure or, relapse of Pelvi- abdominal infection will be recorded
- Subjects will be asked to come after 15 days of the treatment (Day 15) for follow up, with window of 3 days
- In case of any premature discontinuation of the study, the subject will be, if possible, called in for a last visit. Even if the subject was not able to attend the last visit, the End of Study Form must be completed.
- In case of complete resolution, end of the study lab testing will be asked and recorded and End of the study Form will be completed

12.3.3 Follow-up 2 Visit & End of Study Visit (Day 15):

It is the end of study visit for subjects.

The following procedures will be done during this visit, and all relevant information will be recorded in the source document and forms:

- Subjects will undergo thorough general physical examination and Vital signs
- Presence of any signs/symptoms of post-operative wound infection such as redness, fever or wound discharge will be recorded (in case of post-operative subjects)
- Any changes in concomitant medication, illness and treatment will be recorded.
- Checking if any AE or SAEs happened and recording them in their separate forms. Days for complete healing will be checked.
- Complete resolution, improvement, failure or, relapse of Pelvi- abdominal infection will be recorded
- Lab results will be checked for: S. Creatinine, Total leukocytes count, Liver enzymes (SGOT, SGPT), and total bilirubin
- Pelvi-abdominal Ultrasound and others will be done, if needed.
- The End of Study Form must be completed.

13 Management & Reporting of Adverse Events

The physician is responsible for the safety of the patient. The sponsor is responsible for the safety of his product and for reporting safety issues to the regulatory bodies according to appropriate regulations. In order for all parties to comply with their responsibilities, it is important that the physician documents and processes quality and safety issues in the following manner.

13.1 Adverse Events (AEs):

An AE is any undesirable medical event occurring to a subject in a clinical trial, whether or not considered related to the trial product(s). This includes events not seen at baseline or worsened if present at baseline. The following will not be recorded as AEs, if recorded at screening visit: Pre-existing conditions found as a result of screening procedures.

Assessment of Intensity/Severity:

The intensity or severity of an AE is defined as follows :

- Mild: Transient symptoms, no interference with the subject's daily activities.
- Moderate: Marked symptoms, moderate interference with the subject's daily activities.
- Severe: Considerable interference with the subject's daily activities, unacceptable

Assessment of Causality (as per WHO-UMC)

The **relationship** of each AE to the study drug where there is a demonstrable cause-effect association between two events, assessed by the investigator:

Causality Term	Assessment of Causality
Certain	
 •Event or laboratory test abnormality, with plausible time relationship to drug intake •Cannot be explained by disease or other drugs •Response to withdrawal plausible (pharmacologically, pathologically) •Event definitive pharmacologically or phenomenological (i.e. an objective and specific medical disorder or a recognized pharmacological phenomenon) • Re-challenge satisfactory, if necessary
Probable /Likely	
 •Event or laboratory test abnormality, with reasonable time relationship to drug intake •Unlikely to be attributed to disease or other drugs •Response to withdrawal clinically reasonable • Re-challenge not required
Possible	
 •Event or laboratory test abnormality, with reasonable time relationship to drug intake •Could also be explained by disease or other drugs •Information on drug withdrawal may be lacking or unclear
Unlikely	
 •Event or laboratory test abnormality, with a time to drug intake that makes a relationship improbable (but not impossible) •Disease or other drugs provide plausible explanations
Conditional/ Unclassified	
 •Event or laboratory test abnormality •More data for proper assessment needed, or additional data under examination
Un-assessable /Unclassifiable	
 •Report suggesting an adverse reaction •Cannot be judged because information is insufficient or contradictory •Data cannot be supplemented or verified

Outcome categories

The outcome of each AE is recorded on the CRF, according to the following definitions :

- Death Related to Adverse Event: if the termination of life as a result of an adverse event.
- Not Recovered or Not Resolved: to indicate that the event has not improved or recuperated.
- Recovered or Resolved: if the event has improved or recuperated.
- Recovered or Resolved with Sequelae: if the subject recuperated but retained pathological conditions resulting from the prior disease or injury.
- Recovering or Resolving: if the event is improving but has not yet fully recovered
- Unknown: if the outcome was not known, not observed or not recorded

Clinical Laboratory Adverse Events (CLAEs)

A Clinical laboratory AE is any abnormal clinical laboratory value that suggests a disease and/or organ toxicity and is of a severity, which requires active management i.e. change of dose, discontinuation of drug, more frequent follow-up or diagnostic investigation.

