After oral administration, Ciprofloxacin is well absorbed from the abdominal tract. Oral bioavailability is approximately 70 %^[17] and a peak plasma concentration of about 2.5 mcg per ml is achieved after 1 to 2 hours after a dose of 500 mg by mouth. Metronidazole is rapidly absorbed, 80 % is absorbed in one hour. The peak concentration is achieved after 1 to 2 hours after the oral administration. Metronidazole passes the placenta and the maternal milk. The essential excretion is through the liver and the bile. They are absorbed readily and almost completely from the gastrointestinal tract. Serum concentrations reach their peak within one hour of oral ingestion.

Ciprodiazole is contraindicated in the following conditions:

- Hypersensitivity to ciprofloxacin or other antibiotics of Quinolones group such as Ofloxacin, Norfloxacin, Trovofloxacin, and Ofloxacin.
- Hypersensitivity to the metronidazole or other nitroimidazole derivatives
- Children and adolescents below 16 years.
- Epilepsy or other seizure disorders.

- Patients with Glucose-6-Phosphate Dehydrogenase (G6PD) enzyme deficiency.

Sponsor will provide the study treatment for the patients' whole duration according to regulation of Local Health Authorities involved in the product supply since the drug is being used according to the approved marketing label.

The investigator and the research team must evaluate all adverse events and laboratory abnormalities during the study.

A drug-related toxicity or laboratory value outside of the reference range; that is judged by the investigator as having a "reasonable possibility" of being related to the study drug; will be considered as an adverse event.

Drug-Toxicity is deemed "clinically significant" based on the medical judgment of the investigator. Laboratory abnormalities will be managed as deemed clinically appropriate by the investigator until resolved.

The investigator should ensure that any study drug interruptions or dose modifications and associated adverse events are promptly entered into the medical records.

8.2 Ciprofloxacin Hydrochloride:

Ciprofloxacin is a synthetic broad spectrum fluoroquinolone antibiotic. It acts by inhibiting DNA gyrase, which is essential in the reproduction of bacterial DNA. This agent is more active against Gram-negative bacteria than Gram-positive bacteria and aerobic organisms commonly encountered in pelvi-abdominal infections. ^[18 - 19]

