10.7.6 Primary Safety analysis

A. Number of participants experiencing Serious Adverse Events (SAEs). [Time Frame: visit 1 to End of study visit].

- Frequency distribution (number & percent) of occurrence of SAEs necessitating a change or discontinuation of treatment. Chi² test will be used to determine *p*-value and significance between the 2 groups.
- Frequency distribution (number & percent) of type and severity of SAEs. Chi² test will be used to determine *p*-value and significance between the 2 groups.

B. Number of participants experiencing Adverse Events (AEs) leading to permanent discontinuation of the study drug. [Time Frame: visit 1 to End of study visit].

- Frequency distribution (number & percent) of causes of treatment discontinuations. Chi² test will be used to determine *p*-value and significance between the 2 groups.
- Frequency distribution (number & percent) of occurrence of AEs necessitating a change or discontinuation of treatment. Chi² test will be used to determine *p*-value and significance between the 2 groups.

- Frequency distribution (number & percent) of type and severity of AEs. Chi² test will be used to determine *p*-value and significance between the 2 groups.

10.7.7 Primary Efficacy analysis:

A. Complete resolution for Pelvi- abdominal infection based on pelvi-abdominal Ultrasound

- Frequency distribution (number & percent) of complete resolution for pelvi-abdominal infection. Chi² test will be used to determine *p*-value and significance between the 2 groups.

B. Complete healing of the post-operative wounds [Time Frame: Follow-up 1 V to End of study visit].

- Frequency distribution (number & percent) of complete healing of the post-operative wounds. Chi² test will be used to determine *p*-value and significance between the 2 groups.
- Frequency distribution (number & percent) of incomplete healing of the post-operative wounds. Chi² test will be used to determine *p*-value and significance between the 2 groups.
- Frequency distribution (number & percent) of no healing of the post-operative wounds. Chi² test will be used to determine *p*-value and significance between the 2 groups.

10.7.8 Secondary Safety analysis:

A. Presence of any signs/symptoms of post-operative wound infection such as redness, fever or wound discharge [Time Frame: visit 1 to End of study visit].

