9.4 Primary End Point

9.4.1 Primary Safety

Table 4 *Number and percent of Adverse Event necessitating a change or discontinuation of treatment among treatment groups*

	Group A (N=156)	Group B (N=156)	p-value
Total No of SAE, N (%)			
SAE1, N (%)			
SAE2, N (%)			
SAE3, N (%)			

Table 5 *Number and percent of Serious Adverse Event among treatment groups*

	Group A (N=156)	Group B (N=156)	p-value
Total No of SAE, N (%)			
SAE1, N (%)			
SAE2, N (%)			
SAE3, N (%)			

Table 6 *Number and percent of causes of treatment discontinuations among treatment groups*

	Group A (N=156)	Group B (N=156)	p-value
Total No of treatment discontinuations, N (%)			
Cause1, N (%)			
Cause2, N (%)			
Cause3, N (%)			

Table 7 *Number and percent of Adverse Event necessitating a change or discontinuation of treatment among treatment groups*

	Group A (N=156)	Group B (N=156)	p-value
Total No of AE, N (%)			
AE1, N (%)			
AE2, N (%)			
AE3, N (%)			

Table 8 *Number and percent of Adverse Event among treatment groups*

	Group A (N=156)	Group B (N=156)	p-value
Total No of AE, N (%)			
AE1, N (%)			
AE2, N (%)			
AE3, N (%)			

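### The single AE severity scale has no grade suited to symptomless laboratory AEs, so the planned severity comparison cannot separate important liver-enzyme or leukocyte abnormalities from trivial ones (minor; cheap to fix)

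*Protocol*

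**What the plan says.** Protocol Section 13.1 introduces one scale for all AEs ("The intensity or severity of an AE is defined as follows") with three grades:

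- The lowest grade is "Mild: Transient symptoms, no interference with the subject's daily activities".
- The middle grade asks for pronounced symptoms together with a medium degree of hindrance in daily life.
- The highest grade is "Severe: Considerable interference with the subject's daily activities, unacceptable".

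No grade mentions a laboratory value, a threshold or the action taken. Later in Section 13.1, under Clinical Laboratory Adverse Events, an abnormal value that suggests disease or organ toxicity is an AE if it "is of a severity, which requires active management i.e. change of dose, discontinuation of drug, more frequent follow-up or diagnostic investigation". Section 8.1 also counts as an AE "A drug-related toxicity or laboratory value outside of the reference range" when the investigator sees a reasonable possibility of a link to study drug. Neither definition asks for symptoms.

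The grades are used in the primary safety analysis. Protocol 10.7.6 (B) and SAP 8.6 (B) both plan "Frequency distribution (number & percent) of type and severity of AEs" with a Chi² test between arms. Protocol 14.2 adds that intensity will be tabulated by treatment, with a repeated AE counted once per subject at its highest intensity. The shell for SAP Table 8 ("Number and percent of Adverse Event among treatment groups") has rows by event type only, and so does Table 5 for serious AEs.

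The protocol names abnormal liver tests (8.2, 8.6) and leukopenia and blood dyscrasias (8.5) as risks of the study drugs.

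**The concern.** Section 13.1 uses severity in two senses. The grading scale means how much the patient feels and is hindered. The laboratory definition means how much management the abnormal value calls for. Only the first sense has grades. A patient with a large symptomless SGPT rise and a patient with a small one would get the same grade, or none, although both values met the definition of a laboratory AE.

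At stake is one component of the primary safety comparison. If the arms differed in important symptomless laboratory AEs, the severity table would show the difference among Mild events or not show it at all. Where no grade fits, the choice falls to an investigator who knows the treatment, because the trial is open label.

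**Working it through.** The point rests on reading the text, and there is no stated figure to reproduce.

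**Step 1. Apply the scale to a symptomless laboratory AE.**

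| Grade | What it requires | Met without symptoms? |
|---|---|---|
| Mild | transient symptoms and no interference | interference part yes, symptom part no |
| Moderate | marked symptoms and moderate interference | no |
| Severe | considerable interference, plus the undefined word unacceptable | no, unless that one word is stretched |

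The result is Mild if the symptom part is ignored, and no grade if it is not. Symptomatic events such as jaundice can be graded as written.

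**Step 2. See which other analyses would pick such an event up.**

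- *AEs that change or stop treatment* (10.7.6 B; SAP 8.6 B; Tables 6 and 7) are compared without using the grade. A symptomless enzyme rise that stops the drug is counted there.
- *Timing.* Scheduled laboratory tests after baseline take place only at the end-of-study visit: Day 15 ± 3 days, or Follow-up 1 (Day 8) if complete resolution ends the study there (12.3, 12.3.2, 12.3.3). Treatment lasts at most 15 days. The earliest Day 15 visit is Day 15 − 3 = Day 12, so at most 15 − 12 = 3 days of treatment remain. A value first found then will usually lead to follow-up or investigation, which makes it an AE under 13.1 but keeps it out of the change-or-stop comparison.
- *Laboratory endpoints* (10.7.8; SAP 8.8) are tested on mean change. In an arm of 156, one patient's rise of x units moves the arm mean by x/156. Sections 10.7.8 and 8.8 list minimum and maximum among the descriptive statistics, but SAP Tables 12 to 14 show only mean ± SD and percent change. No analysis counts patients with a large abnormality.
- *Table 8* would list the event by type, whatever its size.

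For an important abnormality first found at the last visit, the severity grade is therefore the main planned means of separating it from a trivial one.

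**Step 3. Illustrate the consequence.** The documents give no AE rates, so the rates here are assumptions. Let p1 and p2 be the true proportions of patients with a non-mild AE, n = 156 per arm, two-sided 5% level. Let a share s of those events be symptomless laboratory AEs recorded as Mild, so that the observed rates are p(1 − s). With p̄ the mean of the two observed rates:

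power = Φ{ [ |p2 − p1| − 1.96 √(2p̄(1 − p̄)/n) ] / √( [p1(1 − p1) + p2(1 − p2)]/n ) }

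Worked case, 5% v 15%, s = 0: p̄ = 0.10; first root √(2 × 0.10 × 0.90/156) = 0.03397; second root √((0.0475 + 0.1275)/156) = 0.03349; (0.10 − 1.96 × 0.03397)/0.03349 = 1.00; power 84%.

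| True non-mild rates | s = 0 | s = 25% | s = 50% | s = 75% |
|---|---|---|---|---|
| 5% v 15% | 84% | 71% | 53% | 29% |
| 3% v 10% | 71% | 58% | 41% | 23% |

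If the whole excess in one arm were symptomless laboratory AEs, the observed non-mild rates would be equal (5% v 5%, or 3% v 3%) and the severity comparison would show no difference.

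**The case against.** The strongest reply is that the event is not lost. A reader might infer that patients who stop the drug for a symptomless enzyme rise vanish from the primary safety results. They do not: the change-or-stop comparison and the table of causes of discontinuation count them, and neither uses the grade. Seriousness is judged under 13.2, which has its own medical-judgment route for important events. All of this stands and confines the point to the severity distribution.

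A reader might also infer that the protocol forces these events to be graded Mild. It does not. Mild asks for transient symptoms, the word unacceptable under Severe is not clearly tied to activities, and Section 8.1 leaves the clinical significance of a toxicity to the investigator. The scale is silent here rather than prescriptive. That still leaves the grade undefined in a primary comparison.

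Nor does the laboratory definition show that every such event is misgraded as Mild. It also covers values needing only closer follow-up or a diagnostic test, and for some of those Mild may be fair. The difficulty is that the scale cannot tell these from the others.

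Severe neutropenia is a tempting example, but the scheduled test is the total leukocyte count, with no differential listed. The point should be made for leukocytes and liver enzymes.

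Finally, the missing severity rows in Tables 5 and 8 do not mean that severity will go unreported, because Protocol 14.2 commits to tabulating intensity by treatment. Those rows are only a gap in the shells.

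**Conclusion.** The concern holds in limited form. Section 13.1 defines laboratory AEs by need for management but grades all AEs by symptoms and activity, so a symptomless laboratory AE is Mild at most or has no grade. The planned severity comparison cannot single out the important ones. The other primary safety comparisons, the seriousness criteria and the tests of mean laboratory change are unaffected.

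The severity is minor. The gap bears mainly on abnormalities found at the end-of-study tests. How many there will be cannot be known from the documents, and the power figures show only the direction and possible range under assumed rates and a Mild versus non-mild split.

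One further assumption: the severity line is listed in part B, whose title refers to AEs leading to permanent discontinuation. I read it as covering all AEs, in keeping with the primary safety endpoint and Table 8. If it covers only discontinuing AEs, the gap would fall mainly on the intensity tabulation in 14.2.

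**What to change.** - Reconcile the two parts of Protocol 13.1: state that laboratory AEs are graded by the size of the abnormality on a published laboratory toxicity scale. The sponsor should choose and name the scale before database lock and, as the trial is open label, preferably before laboratory values are tabulated by arm.
- State how a value already abnormal at baseline is graded. Entry is allowed with SGOT and SGPT up to 2 times normal, and 13.1 counts worsening from baseline as an AE.
- Keep the present activity scale for symptomatic AEs, and do not tie the grade to whether the drug was changed or stopped, since that would repeat the comparison already in part B.
- Add mild, moderate and severe rows (patients, at maximum intensity) to SAP Tables 5 and 8, to match SAP 8.6 and Protocol 14.2.

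The cost is a short wording change in the protocol and CRF guidance, and three rows in each of two tables. There are no new tests, visits or patients, because the laboratory values are already collected at baseline and end of study. The documents do not say whether reference limits are recorded in the CRF, but the enzyme exclusion criterion already depends on them. The small downside is two grading scales instead of one.
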